7.5.1 Mark Anatomical Sites

Using a pen or skin marker, with the subject standing upright and bearing weight on the limb being measured, mark the subject at the lateral aspect of the leg 18 cm from the floor (see Figure 2), at the popliteal, and 10 cm from the popliteal (Figure 3).

[figure not shown]

Figure 2. Site A is 18 cm from the floor on lateral aspect of the leg.

[figure not shown]

Figure 3. Site B is the popliteal and Site C is 10 cm above the popliteal.

7.5.2 Circumference Measurements

After marking the anatomical sites, measure and record the circumference, in cm, at sites A (see Figure 4) and C (see Figure 5). The tape measure must be placed precisely over (covering) the skin marking. Adjust the tension of the tape measure so that one red ball is visible in the tension indicator and record the circumference measurement.

Figure 4. Site A circumference measurement.

[figure not shown]

Figure 5. Site C circumference measurement.

7.6 Photograph (Legs)

A digital photograph of the subject's legs will be taken at each study visit. The subject's legs should be exposed, at minimum, from the bottom of the ankle to the mid-thigh. Subjects should sit and straighten their legs as much as possible (see Figure 6).

Figure 6. Leg photograph example.

Additionally, if a subject has areas of hyperpigmentation, ulcers, or excessive swelling, a close-up photo of that area should be taken. The image number(s) from the digital camera should be recorded on the subject's source documentation.

7.7 Prescribed Care & Treatment Protocol

At each visit, current lymphedema treatment, including Flexitouch treatment, will be reviewed and recorded.

7.8 Medication Review

At each clinic visit, use of the following medications will be documented:

- Beta blockers
- Diuretics
- Oral steroids
- Non-Steroidal Anti-Inflammatory Drugs (NSAIDs)

7.9 QoL Questionnaires

The LYMQOL is an assessment tool designed for measuring QoL in patients with lower limb lymphedema.⁹ It is a 25 item questionnaire which has been designed and validated in patients with chronic edema and covers 4 domains: function, appearance, symptoms, and mood and in addition has an overall QoL score. This tool has been designed and validated for patients with chronic lymphedema in one or both legs to measure QoL. (Appendix A)

The Short Form-36 (SF-36) is an assessment of functional status and quality of life. The SF-36 is a validated QoL tool that has been widely utilized and has been found to be appropriate for use in evaluating health related quality of life impacts. The SF-36 consists of 36 questions that evaluate eight health concepts including physical functioning, role functioning-physical, bodily pain, general health, vitality, social functioning, role functioning – emotional, and mental health. (Appendix B)

7.10 Flexitouch Compliance Assessment & Subject Diary

At each phone call and clinic visit, subject compliance will be assessed by collecting the following information:

- Days Flexitouch used in past week
- Days compression garments used in past week
- Difficulty in following treatment
- Difficulty in putting on Flexitouch garments
- Difficulty using Flexitouch controller
- Pain or discomfort experienced when using Flexitouch
- Position treatment being done in

If the subject reports difficulty following treatment, putting on the Flexitouch garment, difficulty using the Flexitouch controller, or is experiencing pain or discomfort when using Flexitouch, the site may refer the subject to Tactile Medical clinical services for assistance in addressing the issue(s).

In addition, the subjects will be provided with a Subject Diary at their Screening/Baseline visit and be instructed to begin completing the diary when they start using their device after their training visit. The subject will be asked to keep a daily record of their use of Flexitouch, Actitouch (if prescribed), and compression stockings. (Appendix C) Subjects should bring their diary into each study visit for review and collection.

If the subject is noncompliant or partially compliant in device use, (see Table 1), the site should identify barriers to compliance and determine if additional device training by the site or Tactile personnel is warranted. If noncompliance continues, the Investigator may initiate the subject's withdrawal from the study.

At the 4 week in-clinic follow-up visit, if a subject is not using their Flexitouch an average of 3 times per week, they will be considered a screen failure.

If the subject experiences a complication (e.g., active infection, DVT) that requires temporary discontinuation of device use and 4 weeks of continuous treatment is not possible before the final in-clinic visit takes place, the subject should be withdrawn from the study.

Additionally, a device history log may be downloaded periodically from Flexitouch Plus units.

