5.1 Study Endpoints

5.1.1 Primary Endpoints

The following primary endpoints for this study will compare changes after 12 weeks of treatment to baseline for the following parameters:

- QoL
- Lymphedema symptoms

In addition, the number of occurrences after 52 weeks of treatment will be compared to the number of occurrences in the year preceding treatment for the following variable:

- Lymphedema and venous related health care utilization

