5.2.3 Subject Withdrawal or Early Termination

Subjects will exit the study if they meet any of the following criteria:

- Subject death
- Subject voluntarily withdraws
- Subject acquires one or more of the exclusion criteria whereby the investigator deems study discontinuation a necessity
 - If subject acquires an infection, they may be treated for the infection and continue in the trial at the investigator’s discretion. Detailed information regarding the infection, nature, treatment, and duration will be recorded.
- Subject diary shows an unwillingness to remain partially compliant or compliant with prescribed care (subject will be considered a screen failure if he or she uses the device <3 times per week on average at the Week 4 visit).

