6.2 Week 0/Training

- The subject will receive the Flexitouch system or Flexitouch Plus and be instructed on use from a Tactile Medical trainer. Device treatment will commence following the visit from the trainer.

6.3 Weeks 1 (+7 days), 18, 32, & 40 (± 14 days) Follow-up Phone Calls

- Prescribed care and treatment protocol
- Medication review
- Flexitouch compliance assessment
- Complication, adverse event, and device observation assessment

6.4 Weeks 4, 8, 12 (± 7 days), 24, and 52 (± 14 days) In-Clinic Follow-Up Visit(s)

- Weight (kg)
- Skin assessment
- Limb circumference
- Photographs (Leg)
- Prescribed care and treatment protocol
- Medication review
- QoL Questionnaires (Weeks 12, 24, and 52 only)
 - LYMQOL
 - SF-36
- Subject diary collection
- Flexitouch compliance assessment
- Complication, adverse event, and device observation assessment

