7.11 Lymphedema and Venous Related HCU, Device-Related Adverse Events, & Device Observations

At each phone call and clinic follow-up visit, assessment of lymphedema and venous related HCU, device-related adverse events, and device observations will occur and be recorded in Clindex, per the following definitions.

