7.11.1 Lymphedema and Venous Related HCU

Lymphedema and venous related visits that required HCU (includes clinic visits, hospitalization, walk-in clinic/urgent care, and ER visits).

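### Late complications lead to study withdrawal under 7.10, and the plan does not say how HCU is collected or analysed for those subjects, although it is compared with a full prior year

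*Combined protocol and SAP*

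**What the plan says.** Section 7.10 covers a complication (infection and DVT are its examples) that forces a temporary stop in device use. If "4 weeks of continuous treatment is not possible before the final in-clinic visit takes place, the subject should be withdrawn from the study".

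Section 5.2.3 lists a further, discretionary exit: "Subject acquires one or more of the exclusion criteria whereby the investigator deems study discontinuation a necessity". For infection it adds: "If subject acquires an infection, they may be treated for the infection and continue in the trial", at the investigator's discretion, and "Detailed information regarding the infection, nature, treatment, and duration will be recorded". Neither section refers to the other.

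Section 5.1.1 makes lymphedema and venous related HCU a primary endpoint: "the number of occurrences after 52 weeks of treatment will be compared to the number of occurrences in the year preceding treatment". Section 7.11.1 defines the visits that count: "includes clinic visits, hospitalization, walk-in clinic/urgent care, and ER visits".

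Collection is tied to contacts (7.11): "At each phone call and clinic follow-up visit, assessment of lymphedema and venous related HCU". The schedule in 7.13 has nine follow-up contacts, the last two being the week-40 call and the week-52 visit. It has no exit visit. Section 9.1 deals with the care of someone who ends participation, not with their data. Section 13.1 gives no analysis set, person-time or rule for withdrawn subjects. The synopsis speaks of a complication rate, but neither 5.1.1 nor 13.1 supplies a denominator.

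**The concern.** The event that triggers withdrawal is closely tied to the outcome. A limb infection or DVT late in the year would normally generate the clinic, hospital or urgent-care visits that the endpoint counts, and under 7.10 it also ends the subject's time in the study. Any care that follows is then outside the contacts at which HCU is recorded. The prior-year count is taken by history at baseline (7.2), before any such exit, so the loss falls on one side of the comparison. With a single arm, no control group shares it. Care that was never recorded cannot be restored by a model.

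**Working it through.** **Inputs from the documents.** The 4-week requirement (7.10), final visit at week 52 ± 14 days, last earlier contact at week 40 ± 14 days (6.3, 6.4, 7.13), and counts compared over one year each (5.1.1). No event rate, pause length or visit frequency is given, so there is no planned figure to reproduce.

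**Assumptions (not in the documents).** No device effect. Pausing complications 0.1, 0.3 or 0.6 per year; 1-4 HCU visits per complication, the first at onset and any others at onset or spread evenly over the pause; 1 or 3 other HCU visits per year; pause of 2, 4 or 8 weeks; a gamma subject effect of shape 1 or 2. Central case: 0.3 per year, 1 other visit, shape 1, 4-week pause, extra visits spread.

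**Step 1: when the rule acts.** A pause of D weeks triggers it if onset + D + 4 > 52, that is, onset after week 48 − D: week 46, 44 or 40 for D = 2, 4, 8. The final-visit window moves these by up to 2 weeks either way.

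**Step 2: share withdrawn.** 1 − (1 + m/k)^(−k), with m = rate × (D + 4)/52 and k = shape.
- Low: m = 0.1 × 6/52 = 0.0115, k = 1: 1.1%.
- Central: m = 0.3 × 8/52 = 0.0462, k = 1: 4.4%. With a week-54 visit, m = 0.3 × 6/52 = 0.0346: 3.3%.
- High: m = 0.6 × 12/52 = 0.138, k = 2: 12.5%.

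**Step 3: HCU captured relative to everyone retained, central case, triggering visit counted.** Let v be visits per complication. The retained total is 1 + 0.3v − 0.3(v − 1) × 2/52; the last term removes visits falling after week 52. The factor 2 for other visits below is the mean square of the gamma effect at shape 1.
- *Leaving at onset.* On average 4 weeks are lost. Extra visits are all lost for onsets in weeks 44-48 and half lost for weeks 48-52, so 0.75 of them. Loss = 0.0462 × [0.75(v − 1) + 2 × 4/52]. For v = 2: 0.0462 × 0.904/1.588 = 0.026, so 0.974. For v = 4: 0.0462 × 2.404/2.165 = 0.051, so 0.949.
- *Leaving only once fewer than 4 weeks remain* (the later of onset and week 48). On average 3 weeks and half the extra visits are lost. For v = 2: 0.0462 × 0.615/1.588 = 0.018, so 0.982. For v = 4: 0.0462 × 1.615/2.165 = 0.034, so 0.966.

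Simulation, which also allows second complications, gives:

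| Final visit | Leaves | v = 1 | v = 2 | v = 4 |
|---|---|---|---|---|
| Week 52 | at onset | 0.993 | 0.972 | 0.948 |
| Week 52 | later | 0.995 | 0.981 | 0.965 |
| Week 54 | at onset | 0.996 | 0.982 | 0.966 |
| Week 54 | later | 0.998 | 0.991 | 0.982 |

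The largest loss on the grid (0.6 per year, 1 other visit, shape 1, 8-week pause, 4 spread visits, week-52 visit) leaves about 0.90 at onset and 0.95 later.

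**Step 4: poorer recording.** If the triggering visit is missed as well, the lowest grid value with exit at onset is 0.86. A second simulation used 0.1-0.4 complications per year with one visit each, 1 other visit per year, pauses of 2, 6 or 13 weeks and exit at onset. It was run with and without heterogeneity plus a tripling of other visits for D + 4 weeks after a complication. The follow-up/prior-year ratio, truly 1, was 0.92-1.00 with HCU recorded to exit, 0.89-0.99 in completers only, and 0.84-0.99 with HCU known only to the last scheduled contact.

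**Step 5: does an offset repair it?** In that second simulation, with HCU recorded to exit, a person-time offset gave 0.999-1.004 without heterogeneity or a rise after a complication, but 0.939-0.994 with both. Collecting HCU to week 52 gave 0.996-1.004 throughout.

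**Step 6: exits under 5.2.3.** Their frequency is unknown. In the central case each 1% of subjects exiting removes about 0.75-1.0% of follow-up HCU with visits at onset, or 1.4-2.4% with 2-4 visits spread.

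**The case against.** **The gaps are silences.** A reader might infer that the plan forbids HCU collection after withdrawal. It does not; it ties collection to scheduled contacts and says nothing more. What stands is that sites have no instruction to collect.

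**Withdrawal may come late, or not be known.** Exit at onset assumes that the site already knows how long the pause will last. Often it becomes clear that 4 weeks will not fit only when fewer than 4 remain, which roughly halves the largest loss. With a week-52 visit, the cut-offs for 2- and 4-week pauses (weeks 46 and 44) also fall after the week-40 call, even if that call is 14 days late. Unless someone reports the event, the site learns of it at the final visit; if HCU is recorded there, little is lost. Both points stand, so the exit-at-onset figures are an upper end for the case where the triggering visit is counted.

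**Infected subjects may continue under 5.2.3.** That provision is discretionary, covers infection only and is not reconciled with 7.10. The infection details it requires are not an HCU count and do not reach past exit.

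**Other errors are as large.** Counting to the final visit covers 50/52 = 0.96 to 54/52 = 1.04 of a year. Nine follow-up contacts against one baseline history may raise the follow-up count, while entry exclusions remove some prior-year events. A reader might conclude that the HCU result is biased in the device's favour overall. The documents do not support that; only this one component has a known sign.

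**The rule may have a purpose.** It plausibly protects the week-52 assessments from subjects recently off treatment. That argues for care with QoL, not for losing HCU.

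**Conclusion.** The concern holds in limited form. The stated rule removes subjects through events that would normally count in a primary endpoint, and the plan gives no instruction for collecting or analysing their HCU. Other things equal, this lowers the follow-up count.

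For the 7.10 rule alone it is minor to moderate: losses of about 1-5% of follow-up HCU in the central case and 5-10% in the largest-loss cell, depending on when subjects leave, with the triggering visit counted and a final visit at week 52. Loss is near zero if the event surfaces and is recorded at the final visit. It is larger if the triggering visit is missed or withdrawn subjects are dropped. Exits under 5.2.3 add an unknown amount. Every figure rests on assumed rates, so none predicts this trial's bias.

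**What to change.** 1. In 7.10 and 5.2.3, separate stopping the device from leaving data collection. Consenting subjects stay in the contacts already scheduled, for HCU and safety, to week 52, with device status recorded; the home-visit option in 6.0 is available for those unable to attend. For anyone who leaves, record HCU to the exit date, including the visit that led to exit. Decisions on device use are unchanged. If QoL is also collected off device, flag it and report week-52 QoL with and without those records, because it changes what that secondary endpoint measures.
2. In 5.1.1 and 13.1, analyse HCU as a within-subject rate with observed person-time, in all trained subjects with any follow-up. Run the set without week-4 screen failures, and completers only, as sensitivity analyses: the week-4 exclusion is itself made after treatment starts. The offset supplements continued collection and should not be presented as removing the bias.
3. Reconcile 5.2.3 and 7.10 for a subject with infection. Which rule should apply is for the sponsor and investigators.
4. Report exits by reason and week.

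The cost is protocol, consent and analysis-plan wording with IRB review, and a few contacts that already exist, for about 1-13% of subjects under the assumed rates for the 7.10 rule plus an unknown number of 5.2.3 exits. The downsides are a possibly less favourable HCU estimate and, if QoL is continued, a mixed on- and off-device population at week 52.

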7.11 Lymphedema and Venous Related HCU, Device-Related Adverse Events, & Device Observations

At each phone call and clinic follow-up visit, assessment of lymphedema and venous related HCU, device-related adverse events, and device observations will occur and be recorded in Clindex, per the following definitions.

7.11.1 Lymphedema and Venous Related HCU

Lymphedema and venous related visits that required HCU (includes clinic visits, hospitalization, walk-in clinic/urgent care, and ER visits).

7.11.2 Device-Related Adverse Events

Any untoward medical occurrence in a subject that is associated with the use of the Flexitouch device.

7.11.3 Device Observations

All subject-reported user errors, device failures, malfunctions, or device issues.

7.12 Flexitouch Administration & Training

After the subject's screening/baseline visit, Tactile Medical personnel will perform in-home device training. The date of device training (Day 0) will be used to determine the timing of subsequent follow-up visits.

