7.2 Demographics & Medical History

Demographics will be collected at baseline including the date of birth, ethnicity, race, gender, and employment status.

If the subject is female and of childbearing potential, a urine pregnancy test will be performed to ensure the subject is not pregnant. Per exclusion criterion 11, if a subject is pregnant or a women of childbearing potential not on contraception, they will be excluded from the study.

Significant medical history and lymphedema history will be collected at baseline including number of lymphedema and venous related visits that required health care utilization (HCU) (includes clinic visits, hospitalization, walk-in clinic/urgent care, and ER visits).

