7.13 Study Schedule of Activities

Assessments	Screening/Baseline	Training / Day 0	Week 1 (Phone Call)	Week 4	Week 8	Week 12	Week 18 (Phone call)	Week 24	Week 32 (Phone call)	Week 40 (Phone call)	Week 52
Visit Window	N/A	N/A	+7 Days	±7 Days	±7 days	±7 days	±14 days	±14days	±14 days	±14 days	±14 days
Informed Consent	X										
Inclusion/Exclusion	X										
Demographics	X										
Medical History/Status	X ¹										
Vital Signs² (Height, Weight)	X			X	X	X		X			X
Skin Assessment	X			X	X	X		X			X
Limb Circumference	X			X	X	X		X			X
Photograph (Leg)	X			X	X	X		X			X
Prescribed Care & Treatment Protocol	X		X	X	X	X	X	X	X	X	X
Medication Review	X		X	X	X	X	X	X	X	X	X
Quality of Life Assessments	X					X		X			X
Subject Diary	X ³			X	X	X		X			X
Flexitouch Compliance			X	X	X	X	X	X	X	X	X
HCU, Adverse Events, & Device Observations			X	X	X	X	X	X	X	X	X
Flexitouch Training		X									

¹Includes Lymphedema History

²Height and weight collected at Screening/Baseline, weight collected at all subsequent visits

³Dispense and train subject on subject diary completion

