8.0 Study Device Accountability

To participate in the study, the Flexitouch must be covered by a payer. The Flexitouch will be provided to the subject and tracked according to normal business practices. Subjects' whose payer requires rental of the Flexitouch will be excluded from the study.

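### Prior health care utilization is counted once at screening, but treatment starts at a later training visit with no limit on the interval, so visits in between have no assigned period in the primary HCU comparison

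*Combined protocol and SAP*

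**What the plan says.** For lymphedema and venous related HCU, section 5.1.1 states that "the number of occurrences after 52 weeks of treatment will be compared to the number of occurrences in the year preceding treatment". The boundary between the two periods is therefore the start of treatment. In the same section, the QoL and symptom endpoints "will compare changes after 12 weeks of treatment to baseline for the following parameters".

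The prior HCU count comes from the history. Section 7.2 reads: "Significant medical history and lymphedema history will be collected at baseline including number of lymphedema and venous related visits that required health care utilization". It gives no look-back length. Sections 6.1 and 7.13 also place the SF-36 and LYMQOL at Screening/Baseline; the next QoL assessment is at Week 12 (section 6.4).

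Treatment does not start at that visit. Section 7.12 puts home training after it and adds: "The date of device training (Day 0) will be used to determine the timing of subsequent follow-up visits". Section 6.2 has device use begin once the trainer has visited. Section 7.10 also treats the two dates as different: the diary is handed out at screening but not filled in until device use starts.

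In the schedule (section 7.13), the visit window is N/A for both Screening/Baseline and Training, and the only entry under Training is the training itself. The row "HCU, Adverse Events, & Device Observations" starts at Week 1. Section 7.11 has HCU asked at each call and follow-up visit but does not say from what date the subject should recall. Section 13.1 gives no rule for assigning visits to periods.

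**The concern.** By section 5.1.1, a visit after screening and before Day 0 is a pre-treatment event. The pre-treatment count has already been taken by then, and nothing updates it. Such a visit either goes unrecorded or is mentioned at the Week 1 call, where no recall start date stops it from being entered as on-treatment. Sites and subjects may differ in which happens.

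The trial has a single arm, so before against after is its only overall contrast, and assignment to the two periods matters more than it would with a control group. If gap visits enter follow-up, a real reduction in HCU could be hidden.

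A secondary point concerns QoL. The change from baseline to Week 12 includes the untreated gap, so it covers more than 12 weeks of treatment. Any drift, regression to the mean or effect of other care during the gap becomes part of the measured change.

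**Working it through.** The plan has no figure of its own to reproduce. Section 13.2 describes up to 300 subjects as a sample of convenience, and no HCU rate, effect size, alpha or power is given.

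**Inputs from the protocol**
- On-treatment period: 52 weeks from Day 0 (sections 5.1.1 and 7.12).
- Pre-treatment period: one year, taken as 52 weeks (section 5.1.1).
- QoL follow-up: Week 12, counted from Day 0 (sections 5.1.1 and 7.13).

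**Assumptions**
- The gap from screening to Day 0 is g weeks. Its length is not given, so I use 1, 2, 4, 8 and 12.
- The visit rate is constant while untreated.
- The history at screening covers a full 52 weeks ending at screening. Section 7.2 does not say so.

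**Formulas**
- Share of the defined pre-treatment year not observable at screening: g/52.
- Post/pre HCU ratio with no device effect, gap visits counted in follow-up: (52 + g)/52.
- The same with a true 10% reduction on treatment: (52 × 0.90 + g)/52.
- Untreated share of the baseline-to-Week-12 QoL interval: g/(12 + g).

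| Gap (weeks) | Pre-year not observable | Ratio, no effect | Ratio, true 0.90 | QoL interval (weeks) | Untreated share |
|---|---|---|---|---|---|
| 1 | 1/52 = 1.9% | 53/52 = 1.02 | 47.8/52 = 0.92 | 13 | 7.7% |
| 2 | 2/52 = 3.8% | 54/52 = 1.04 | 48.8/52 = 0.94 | 14 | 14.3% |
| 4 | 4/52 = 7.7% | 56/52 = 1.08 | 50.8/52 = 0.98 | 16 | 25% |
| 8 | 8/52 = 15.4% | 60/52 = 1.15 | 54.8/52 = 1.05 | 20 | 40% |
| 12 | 12/52 = 23.1% | 64/52 = 1.23 | 58.8/52 = 1.13 | 24 | 50% |

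**If gap visits are lost instead.** The comparison is 52 weeks before screening against 52 weeks after Day 0, and the expected ratio with no effect is 52/52 = 1.00. The observed year differs from the defined one only in that the g gap weeks are replaced by the g weeks just before the defined year begins. The loss is neutral if the rate is the same in both stretches.

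**Length of follow-up.** The Week 52 visit has a ±14-day window. Since 52 × 7 = 364, observation can end anywhere from Day 350 (364 − 14) to Day 378 (364 + 14), so raw counts do not cover equal time.

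**The case against.** The strongest reply is that the gap may be trivial. A prescription is an entry criterion, and what the protocol describes after screening is supply of the device and one home visit. At 1 to 2 weeks, only 1.9% to 3.8% of the year is affected and the ratio moves to 1.02 to 1.04. This stands: the size is unknown and may be small.

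The direction also counts for the defence. Gap visits that enter follow-up work against the device, and lost visits are neutral at a constant rate. Under these assumptions, the mechanism does not create an apparent HCU benefit. This stands too, although hiding a real reduction would also be an error.

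A third reply is that the data may be recoverable. Section 11.5 requires sites to keep full medical records for each subject, and the HCU form is not in the documents, so it cannot be shown that visit dates are missing from it. This stands in part. Some visits could be retrieved, but urgent care or ER visits elsewhere may not be in the site's records, and no rule assigns them once found.

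Three stronger readings are tempting but not supported:
- A reader might infer that payer approval falls between screening and training and makes the gap long. Section 8.0 says only "To participate in the study, the Flexitouch must be covered by a payer" and gives no timing; cover may be settled before screening.
- A reader might infer that both primary comparisons are broken at Day 0. The QoL comparison is made to a named baseline visit and can be carried out as written.
- A reader might infer that the plan specifies the year before screening. Section 7.2 states no look-back, and the only one-year anchor, in section 5.1.1, is tied to treatment. The plan is under-specified, not set to the wrong year.

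**Conclusion.** The point holds for the HCU endpoint. The schedule as written cannot fully deliver the pre-treatment year that section 5.1.1 defines, because the count stops at screening, treatment starts later, the interval has no limit and nothing is updated at Day 0.

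The effect ranges from slight at 1 to 2 weeks to enough to reverse a true 10% reduction at 8 weeks or more, if gap visits are swept into follow-up. If they are lost, the cost is missing data and a pre-period other than the one defined, with no expected bias at a constant rate. All figures rest on assumed gaps and a constant untreated rate.

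For QoL the point is secondary. The change covers 12 + g weeks, and a single-arm design cannot separate untreated change from device effect at any gap length. This is a weakness that should be repaired, not one that invalidates the study.

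**What to change.** - Record the date of each HCU visit, both in the baseline history and in follow-up.
- At the existing Week 1 call, ask separately about visits between screening and Day 0, and assign them to the pre-period.
- State in sections 5.1.1 and 7.2 that the pre-period is the 365 days before Day 0. Count on-treatment HCU only from Day 0, and express it per observed person-time because of the Week 52 window.
- Report the distribution of the screening-to-Day 0 interval.
- Give a sensitivity analysis of the QoL change by gap length.

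With gap visits assigned this way, the unobserved share of the pre-year falls to zero apart from recall error, and the no-effect ratio returns to 52/52 = 1.00 at a constant rate.

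The cost is one extra question at a call already scheduled, visit dates on the HCU form and a little more analysis. I would not add a repeat QoL questionnaire for late starters. Any threshold would be arbitrary, subjects would have baselines taken under different conditions, and the only scheduled contact between screening and first use is the sponsor's trainer, so a repeat would need a new site contact or outcome collection by the sponsor.
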